### **8.2.3. Baseline/Investigational Product Administration: Day 1 – Part B**

Once a subject has signed consent, completed the Screening assessments, met all study eligibility criteria, and completed the Lead-In period, the Day 1 baseline assessments and investigational product administration are performed. Results from the concomitant medications review, urine pregnancy test (for female subjects of childbearing potential), and C-SSRS (“Since Last Visit” version) must be available and reviewed by the Investigator to confirm the subject’s eligibility before randomization. In addition, the following assessments are to be performed on all subjects prior to dosing to establish Baseline status: medical history, vital signs, clinical laboratory tests, tympanometry, audiometry, otoscopy, and TFI. For subjects undergoing Part B PK evaluations, a pre-dose plasma PK sample will be obtained on Day 1 at any time prior to investigational product administration.

If the subject is no longer eligible, the subject will not be randomized and should be recorded as a screen failure. Information related to specific inclusion/exclusion criteria will be documented. Once eligibility status is confirmed and the subject is randomized, the investigational product is

administered and the remaining Day 1 assessments (e.g. PK sampling at 1 hours [ $\pm$  15 minutes] in select subjects, AE monitoring) are completed.

All assessments as listed in the Time and Events Schedule for Part B (Table 2) are to be performed at this visit.

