#### **8.5.1.     **Tinnitus Functional Index (TFI)****

The TFI is a validated, 25-item questionnaire that can be used to scale overall severity of tinnitus and to assess treatment-related change in tinnitus (Meikle et al., 2012; Henry et al., 2015). The 25 items of the TFI represent 8 subscales covering multiple domains of tinnitus severity: 1) Intrusive, 2) Sense of Control, 3) Cognitive, 4) Sleep, 5) Auditory, 6) Relaxation, 7) Quality of Life, and 8) Emotional. Subjects answer each TFI question by rating their experience over the past week.

Completing the TFI provides an index score from 0 to 100, with higher scores representing a greater problem with tinnitus. A reduction in the TFI index score of 13 points or more is considered clinically meaningful improvement in tinnitus (Meikle et al., 2012).

In Part A, subjects will complete the TFI at Screening, Day 1 (pre-dose), and Days 8, 15, and 29.

In Part B, subjects will complete the TFI at Screening, Day 1 (pre-dose), and Days 15, 29, and 57.

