## **11. STATISTICAL METHODS**

### **11.1. Sample Size**

The sample size for Part A (8 subjects) was selected based on clinical judgment and is not based on statistical considerations. For Part B, the assumed true standard deviation (SD) of the change from Baseline to Day 57 in the TFI overall score is 17 points. Based on the use of a one-sided two-sample t test at the  $\alpha=0.05$  level of significance, a sample size of 50 subjects (25 subjects per arm) will provide 80% power to detect a mean difference between groups of 12 points on the TFI.

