#### **11.4.7. Exploratory Efficacy Endpoints**

The exploratory efficacy endpoints for Part B are:

- Change from Baseline in the 7-day average NRS ratings of tinnitus annoyance at Weeks 2, 4, and 8.
- Change from Baseline in the 7-day average NRS ratings of tinnitus loudness at Weeks 2, 4, and 8.
- Change from Baseline in TFI overall score from Baseline at Days 15 and 29.
- The occurrence of at least a 13-point reduction in the overall TFI score from Baseline at Days 15, 29, and 57.
- Change in TFI subscale (Intrusiveness, Sense of Control, Cognitive, Sleep, Auditory, Relaxation, Quality of Life, Emotional) scores from Baseline at Days 15, 29, and 57.
- PGIC scores at Days 8, 15, 29, and 57.

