#### **11.4.8. Analytic Methods for Efficacy**

For Part B, the key primary endpoint (change from Baseline to Day 57 in the TFI overall score) and all exploratory endpoints that are defined in terms of the change from baseline will be analyzed using analysis of covariance (ANCOVA) models with treatment group as a factor and the baseline value of the corresponding endpoint as a covariate. All proportion endpoints will be analyzed using Pearson's chi-square test, provided that the minimum expected cell count is at least 5. Otherwise, Fisher's exact test will be used. Correlations between endpoints will be assessed using the Pearson and Spearman correlation coefficients. All statistical analyses will be conducted using one-sided tests at the  $\alpha=0.05$  level of significance, with no adjustments for multiplicity.

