### **11.6. Handling of Missing Data, Subject Withdrawals, and Treatment Failures**

The SAP will include details regarding the handling of missing data as well as the instructions for scoring the TFI, including handling of missing TFI questionnaire items. Every reasonable effort will be made to encourage compliance with study measurement methods and study procedures to minimize missing data.

Every reasonable effort will be made to follow subjects who withdraw from the study for safety evaluation until the date they would have completed participation.

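### Minor: the exploratory 13-point TFI responder comparison makes no use of baseline TFI, and a baseline-adjusted risk difference would be a cheap, modest gain in precision

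*Combined protocol and SAP*

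**What the plan says.** Section 11.4.8 of the protocol, with matching wording under the Part B analyses in the synopsis, sets two rules for efficacy.

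- Change-from-baseline endpoints get an ANCOVA with treatment as a factor and "the baseline value of the corresponding endpoint as a covariate". Overall TFI change at Days 15, 29 and 57 is therefore adjusted for baseline TFI.
- Proportions, all of them, get a two-group test: Pearson's "chi-square test, provided that the minimum expected cell count is at least 5", with Fisher's exact test as the fallback. No covariate is named. Tests are one-sided at 0.05 without multiplicity adjustment.

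Section 11.4.7 lists the responder endpoint as exploratory: "The occurrence of at least a 13-point reduction in the overall TFI score from Baseline at Days 15, 29, and 57". It is built on a change from baseline, but it is a proportion, so the second rule governs it.

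The covariate is collected in everyone. Section 8.5.1 states "In Part B, subjects will complete the TFI at Screening, Day 1 (pre-dose), and Days 15, 29, and 57", and Section 8.2.3 includes TFI among the pre-dose measures: "the following assessments are to be performed on all subjects prior to dosing to establish Baseline status".

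Section 11.6 refers to a further document: "The SAP will include details regarding the handling of missing data as well as the instructions for scoring the TFI". It does not defer the choice of responder test. No logistic, stratified or otherwise baseline-adjusted responder analysis appears in the text.

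**The concern.** One score, at one visit, from one baseline, is handled in two ways. As a continuous change it is adjusted for baseline TFI. Cut at 13 points, it is not. Section 8.5.1 treats 13 points as the threshold for a clinically meaningful improvement, so many readers will look at the responder result first.

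Part B has 25 subjects per arm, and Section 5.2.3 describes permuted blocks without stating stratification by TFI. Some chance difference in mean baseline TFI is to be expected. If baseline predicts change, that difference adds noise to the unadjusted risk difference, and the noise could be removed with data already in hand. What is at stake is the width of an exploratory interval and its agreement with the ANCOVA of the same score.

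**Working it through.** **The plan's own figure.** Section 11.1 gives 25 per arm, a difference of 12, a one-sided test at 0.05, 80% power, and "assumed true standard deviation (SD) of the change from Baseline to Day 57 in the TFI overall score is 17 points". The normal approximation gives 80.3% and the exact t test on 48 df gives 79.3%. The figure reproduces. It belongs to the continuous endpoint and is not affected by this point.

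**Responder rates implied by those inputs.** Assume a normally distributed reduction and a placebo improvement of 5 points, which is not in the documents.

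- Placebo: 1 - Φ((13 - 5)/17) = 0.319.
- OTO-313: 1 - Φ((13 - 17)/17) = 0.593.
- Standard error of the unadjusted risk difference: √(0.593 × 0.407/25 + 0.319 × 0.681/25) = 0.135.

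**Baseline-change correlation r.** The documents give neither r nor the SDs of TFI at baseline and follow-up, so r is a range.

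- Equal SDs S at baseline and follow-up, with an SD of change of 17, imply r = 17/(2S). That is 0.57 at S = 15 and 0.43 at S = 20.
- A baseline SD of 15 and a follow-up SD of 20 give covariance (225 + 400 - 289)/2 = 168, so r = (225 - 168)/(15 × 17) = 0.22.

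**What a chance imbalance does.** The between-arm difference in mean baseline has SD √(2/25) = 0.28 baseline SDs. An imbalance of that size moves mean change by 0.28 × r in units of its SD. The normal density at the cut is 0.357 for placebo and 0.388 for OTO-313, average 0.373.

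- r = 0.43: 0.283 × 0.43 × 0.373 = 0.045.
- r = 0.57: 0.283 × 0.57 × 0.373 = 0.060.

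This is about 4-6 percentage points, less than half the standard error of 13.5 points.

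**Simulation.** 25 per arm and 20,000-40,000 trials per setting. The planned chi-square/Fisher test is compared with a logistic model of treatment and baseline TFI. The risk difference is standardised over the observed baselines. Matched power holds the adjusted likelihood-ratio test to the unadjusted test's own one-sided size.

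| r | SD of risk difference, unadjusted | adjusted | change | Power, unadjusted | adjusted, nominal 5% | adjusted, matched size |
|---|---|---|---|---|---|---|
| 0 | 0.135 | 0.137 | about +1% | 66% | 64% | 62% |
| 0.22 | 0.136 | 0.135 | under 1% | 66% | 65% | 63% |
| 0.3 | 0.137 | 0.134 | -2% | 66% | 66% | 63-65% |
| 0.43 | 0.135 | 0.128 | -5% | 66% | 68% | 65-66% |
| 0.57 | 0.136 | 0.122 | -9 to -10% | 66% | 72% | 70% |

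Over placebo improvements of 0 to 10, the one-sided size was 5.5-6% for the adjusted likelihood-ratio test and about 4-6% for the unadjusted test. Coverage of a nominal 90% interval was 0.88 for the adjusted risk difference and 0.86 for the unadjusted Wald interval.

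**The case against.** The strongest reply is that nothing here is wrong. ANCOVA for changes with a simple test for proportions is an ordinary pairing. The endpoint is exploratory in a Phase 1/2 study whose Part B primary objective is safety, and the same TFI change is already baseline-adjusted at every TFI visit. All of that stands.

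The second reply is that the power gain is partly an artefact of a liberal test, and this also stands. A reader might infer from 72% against 66% that adjustment buys 6 points of power. At matched size and a placebo improvement of 5, the gain at r = 0.57 is about 4 points. Power is level at 0.43, level or slightly lower at 0.3, and 3-4 points lower at 0-0.22. The sign also depends on the placebo response rate. At a common responder rate near 45% the unadjusted test is itself at 5.7-6.1%, so matching there would favour adjustment more.

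A reader might also infer that the planned test inflates false positives. With a forced imbalance of 0.5 baseline SDs favouring OTO-313 and no true effect, its one-sided error is 11-20% for r = 0.3-0.6, against about 6% adjusted. That figure is conditional on an imbalance of 0.5/0.283 = 1.77 SDs, and one that large or larger in that direction has a chance of about 4%. Averaged over all randomisations, the unadjusted test stays near 5%. The documents do not support a charge of bias or invalidity.

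Finally, the separate SAP might already name the covariate. Section 11.6 does not promise that, but the text reviewed cannot rule it out.

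**Conclusion.** The point holds as a minor, cheap improvement. The plan leaves baseline TFI out of the responder comparison while using it for the same score analysed as continuous. The benefit lies in the precision of the estimated risk difference and in agreement with the ANCOVA. It does not lie in the validity of the test, and a power gain is not assured. The SD falls by about 2% at r = 0.3, 5% at 0.43 and 9-10% at 0.57, with nothing gained near r = 0.

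These figures rest on the plan's SD of 17, difference of 12 and 25 per arm, on an assumed placebo improvement of 5 points, and on an r that the documents do not give. The sample size and the analysis of the Day 57 TFI change are untouched.

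**What to change.** In Section 11.4.8 and the matching synopsis text, add for Days 15, 29 and 57 a logistic regression of response on treatment and baseline TFI overall score, fitted by Firth-penalised likelihood when the minimum expected count is below 5 (the plan's existing switch). Report the risk difference standardised over the observed baseline TFI values, with a two-sided 90% confidence interval to match the one-sided 5% level, as the main responder estimate. Keep the planned chi-square or Fisher test, in its one-sided form, beside it. Settle this before unblinding, so that the adjustment is not chosen after an imbalance has been seen.

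The cost is one extra model at three visits and a few sentences, with no new data. If baseline TFI proves unrelated to change, the SD of the estimate is about 1% larger. Keeping the planned test for inference avoids relying on the slightly liberal adjusted test. If the SAP already specifies this covariate, no change is needed beyond a cross-reference.

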#### **11.5. Safety Evaluations**

Safety endpoints to be examined include:

- Vital Signs and Weight Measurements
- Clinical Laboratory Tests
- Tympanometry
- Audiometry
- Otoscopy
- C-SSRS Assessment
- Concomitant Medications
- Adverse events

Descriptive statistical tabulations will be presented for all subjects included in the Safety Analysis Set.

### **11.5.1. Adverse Events**

The current version of Medical Dictionary for Regulatory Activities (MedDRA), as indicated in the Data Management Plan, will be used to code all AEs.

The primary analysis of AEs will consider only treatment-emergent adverse events (TEAEs), events occurring for the first time, or worsening during or after the first dose of investigational product. Subject incidence of TEAEs and SAEs will be tabulated by Preferred Terms (PTs) and System Organ Class (SOC). Severity and relationship to investigational product will also be presented. For summary tables, a subject who experiences the same coded event more than once is counted only one time for that coded event at the highest severity level. AEs will be presented by descending order of frequency in MedDRA SOC and PT.

Listings of all SAEs, AEs leading to study withdrawal, and deaths on-study will also be included. Duration and outcome of each AE will be reported in subject listings.

Adverse events for the C-SSRS occurring during the Lead-in period prior to exposure to investigational product will be reported in data listings. Further details will be provided in the SAP.

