## **2.2. Part B**

### **2.2.1. Primary objective**

- To evaluate the safety and tolerability of OTO-313 in subjects with unilateral tinnitus.

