#### **9.1.1. Assessment of Severity**

The Investigator will assess the intensity of the AE and rate the AE as mild, moderate, or severe using the following criteria:

**Grade 1 – Mild:** These events are easily tolerated, require minimal or no treatment, and do not interfere with the subject’s daily activities.

**Grade 2 – Moderate:** These events cause sufficient discomfort to interfere with daily activity and/or require a simple dose of medication, e.g., analgesics or anti-emetics.

**Grade 3 – Severe:** These events incapacitate and prevent usual activity or require complex medication/treatment or hospitalization.

**Grade 4 – Life Threatening:** These events are those for which the subject was at risk of death at the time of the event rather than an event which hypothetically might have caused death if it were more severe.

**Grade 5 – Death:** The event resulted in the death of the subject.

Changes in the severity of an AE should be documented to allow for an assessment of the duration of the event at each level of intensity to be performed.

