#### **9.1.2. Assessment of Causality**

The Investigator will assess the relationship or association of the investigational product in causing or contributing to the AE, which will be characterized using the following classification and criteria:

**Definite:** AEs that, after careful medical evaluation, are considered definitely related to the investigational product; other conditions (concurrent illness, progression/expression of disease state, or concurrent medication reaction) do not appear to explain the event.

**Probable:** AEs that, after careful medical evaluation, are considered with a high degree of certainty to be related to the investigational product. The following characteristics will apply:

- a reasonable temporal relationship exists between the event and exposure to the investigational product, and
- the event is a known reaction to the investigational product that cannot be explained by an alternative cause commonly occurring in the population/individual, or
- the event is not a known reaction to the investigational product but cannot be reasonably explained by an alternative cause.

**Possible:** AEs that, after careful medical evaluation, do not meet the criteria for a definite or probable relationship to the investigational product, but for which a connection cannot be ruled out with certainty. The following characteristics will apply:

- the event occurs after exposure to the investigational product, and
- there is a reasonable temporal relationship to the application, but the event is not a known reaction to the investigational product and could be explained by a commonly occurring alternative cause, or
- in the absence of a reasonable temporal relationship, the event cannot be explained by an alternative cause.

**Not related:** AEs in this category will have either of the following characteristics:

- the event does not have a reasonable temporal relationship to investigational product administration and/or can be explained by a commonly occurring alternative cause.

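### The one counting rule for AE summary tables selects by severity; read literally, it can show a repeated event as not related although a milder occurrence was judged related

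*Combined protocol and SAP*

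**What the plan says.** Section 11.5.1 of the protocol tabulates the subject incidence of TEAEs and SAEs by preferred term and system organ class. It then adds: "Severity and relationship to investigational product will also be presented". The next sentence is addressed to summary tables in general and sets the counting rule: "a subject who experiences the same coded event more than once is counted only one time for that coded event at the highest severity level". No type of summary table is exempted.

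Severity and causality are separate ratings of each event. Section 9.1.1 says: "The Investigator will assess the intensity of the AE and rate the AE as mild, moderate, or severe", with the criteria running to Grade 5. Section 9.1.2 says: "The Investigator will assess the relationship or association of the investigational product in causing or contributing to the AE", using four categories: definite, probable, possible and not related.

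For the listings, section 11.5.1 says: "Duration and outcome of each AE will be reported in subject listings". Relationship is not named in that sentence. The section closes with "Further details will be provided in the SAP", at the end of a paragraph about C-SSRS events before dosing. The supplied documents contain no SAP text on counting, no rule for choosing a relationship category when a term recurs, and no rule for ties in severity.

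**The concern.** A rule that picks the worst severity suits a severity table. Applied to a relationship table, it uses the wrong criterion, because the occurrence kept is chosen without regard to causality. If a subject has a mild occurrence judged related and a later, more severe occurrence of the same term judged unrelated, the single count sits at the more severe one. The table then shows the term as not related for that subject.

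Compared with counting at the strongest relationship, the category from the most severe occurrence can be equal or weaker but never stronger, so any distortion goes one way. The table supports a primary objective: Part B is designed "To evaluate the safety and tolerability of OTO-313 in subjects with unilateral tinnitus", and Part A has the matching objective. The design also makes discordant ratings possible. Part B gives one injection on Day 1 and follows subjects to Day 57, and section 9.1.2 makes timing relative to exposure part of the causality judgement, so an early and a late occurrence of one term could be rated differently.

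**Working it through.** The plan states no figure on this point, so there is none to reproduce. The check applies the rule to every possible pattern.

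**Inputs**
- Counting rule: one count per subject per coded term, at the highest severity (11.5.1).
- Severity: Grades 1 to 3 (9.1.1; Grades 4 and 5 left out for simplicity).
- Causality: four categories (9.1.2).
- Part B arm size: 25 (11.1). Part A active group: 6 (5.1).

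**Enumeration**

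One occurrence can take 3 × 4 = 12 severity-by-causality types. Two occurrences of one term in one subject give 12 × 13 / 2 = 78 unordered pairs.

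| Outcome when the most severe occurrence is carried into the relationship table | Count |
|---|---|
| Shown as not related although the milder occurrence was related: 3 pairs of unequal grades × 3 related categories | 9 of 78 |
| Shown at a weaker relationship than the strongest recorded (includes the 9 above): 3 pairs of unequal grades × 6 ways for the milder occurrence to have the stronger relationship | 18 of 78 |
| Equal severity, one related and one not, display undefined: 3 grades × 3 related categories | 9 of 78 |
| Related occurrence lost if the subject is counted at the strongest relationship | 0 of 78 |

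These are counts of patterns, not expected frequencies.

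**Worked case**

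A subject has one term twice: Grade 1 rated probable, and Grade 2 rated not related. The rule gives one count at Grade 2, so the relationship table shows not related. Counting at the strongest relationship shows probable. The all-causality table shows one subject with the term under either rule.

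**Size per affected subject, for that term**
- Part B arm: 1/25 = 4 percentage points. Two subjects give 2/25 = 8 points, and three give 3/25 = 12 points.
- Part A active group: 1/6 = 16.7, or about 17 points.

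The incidence of any related event falls only if the subject has no other event shown as related. The same holds within a system organ class. The documents give no rate of repeated events or of discordant ratings, so the number affected cannot be computed.

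**The case against.** The strongest objection is that the sentence fixes the number of counts and the severity category but does not say outright which relationship goes with the count. Two other readings are possible: the severity phrase governs only the severity display, or a table of related TEAEs first selects related events and then removes repeats. Neither loses the related occurrence. This stands as a limit on certainty. It does not remove the problem, because the rule is addressed to summary tables in general and directly follows the sentence on relationship. If it was meant only for severity, relationship tables have no rule, and the same sentence closes that gap.

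A second objection is that such detail belongs in the SAP. That is fair, and the SAP is a good place for the correction. However, the deferral closes a paragraph on C-SSRS events, its reach over all AE tables is arguable, and no SAP rule is available to check.

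A third objection is that nothing is lost from the data. This is correct for the eCRF, where each event and its causality rating are recorded. Sponsor and CRO medical staff also review all AEs (14.6). A record or listing does not, however, correct an incidence table.

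A reader might infer more than the documents support:
- **That the related event rate is a main output of the primary objective.** The safety endpoints in 11.4.1 and 11.4.4 concern TEAEs as such. Neither is a drug-related rate, and relationship is an additional presentation.
- **That ear terms are especially prone to repeat.** No recurrence rate is given, and treatment is a single injection. Section 9.1.1 also has changes in severity documented within an AE, so a change in grade is not necessarily a second event.
- **That under-reporting is demonstrated.** It requires the same term twice in one subject, recorded as separate events, with discordant causality and the unrelated occurrence more severe. How often that happens is unknown.

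**Conclusion.** The point holds as a minor one. As written, the only counting rule for AE summary tables selects by severity. Carried into the relationship table, it can display not related for a subject with a related occurrence of the same term, and it leaves severity ties with discordant causality unresolved.

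The effect on that term's related incidence is 4 percentage points per affected subject in a Part B arm of 25, and about 17 points in the Part A active group of 6. The total effect is probably small. All-causality TEAE incidence, and with it the comparison with placebo on that measure, does not change.

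The conclusion rests on two assumptions: the rule is read literally as covering the relationship presentation, and the SAP does not already supply a different rule. The documents do not support a stronger claim that related events are systematically lost.

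**What to change.** In section 11.5.1 and the SAP:

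1. Limit the highest-severity rule to severity tables.
2. State that relationship tables count each subject once per coded term at the strongest relationship, in the order definite, probable, possible, not related. This also settles ties in severity.
3. If a severity table of related TEAEs is produced (the protocol does not promise one), select the related occurrences first and then take the highest severity among them.

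The cost is a sentence or two of text and minor table programming. Reported related-event rates may rise slightly. Making the change before unblinding avoids a post hoc choice of counting rule.
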